In light of recent advances in the development of mobile interventions for exercise (Fanning, Mullen, & McAuley, 2012) and evidence that treating physical inactivity concurrently with smoking may increase short-term abstinence above and beyond typical smoking interventions (Spring et al., 2009), we have designed a Smoking Treatment and Exercise Program for Underserved Populations (STEP UP) that uses mobile CM (mCM) to simultaneously promote smoking cessation and physical activity.

The purpose of this pilot project is to evaluate the feasibility, acceptability, and efficacy of STEP UP. Given the heightened prevalence of smoking and physical inactivity among low-income populations, in addition to structural barriers to treatment, we propose to target low-income smokers with this intervention.

Methods

Participants

Participants will be adult men and women who smoke cigarettes. We plan to enroll 15 participants in order to reach a goal of 10 study completers.

Participants will be eligible for inclusion in the study if they meet the following criteria:

- current household income less than twice the federal poverty guidelines (Finer & Henshaw, 2006; for instance, someone from a family of 4 must have a household income less than \$48,500 to be eligible)
- currently smoke >10 cigarettes a day
- smoking for at least the past year
- can speak and write fluent conversational English
- are 18-70 years of age
- are willing to make an attempt to quit smoking and increase physical activity

Participants will be excluded from the study for the following:

- inability to walk
- expected to have unstable medication regimen during the study
- currently receiving non-study behavioral treatment for smoking
- myocardial infarction in the past 6 months
- contraindication to nicotine replacement therapy (NRT) or bupropion with no medical clearance
- exclusive use of other forms of nicotine such as cigars, pipes, e-cigarettes, or chewing tobacco
- current pregnancy

- current imprisonment or psychiatric hospitalization

Recruitment

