Participants will be recruited from outpatient clinics at Duke University Medical Center (DUMC). Flyers and brochures will be placed in DUMC clinic areas, and may also be placed in community settings such as local restaurants and grocery stores. We will also advertise in local newspapers and online classified services such as www.craigslist.com. We will contact administrators and/or clinicians at local area community health centers, including Lincoln Community Health Center, to get permission to provide recruitment materials at those sites. Upon approval by the Durham Veterans Affairs (VA) Medical Center IRB, we will post flyers and brochures at that facility and its community-based outpatient clinics. Any flyer posted at the VA-owned facilities will include the following statement: "This is not VA research, will not be conducted by VA, has not been reviewed by VA's Institutional Review Board, and is not endorsed by VA. VA is not responsible for any costs incurred by a Veteran if the Veteran enters the study as a research subject. The announcement is being provided for information only."

Any participant who contacts by telephone the study coordinator or other study staff regarding the study will be provided more information, and will be interviewed using an IRB-approved telephone screening. We will retain the deidentified telephone screening information for all callers so that we can analyze data regarding telephone screen-outs in order to determine recruitment and inclusion/exclusion feasibility.

Study Procedures

Table 1 provides a summary of study procedures, including the timing and location of each session and payments associated with them.

Table 1. Study Procedures

Session #	Location of Visit	Procedures	Payment
1	Lab	Consent; questionnaires; urine drug screen and pregnancy test; carbon monoxide readings; equipment training; counseling session 1 of 5	\$100
1-3 weeks			
2	Phone	Brief phone check-in for participants using bupropion; begin bupropion if eligible	n/a
1 week			
3	Phone	Counseling session 2 of 5; begin practice mCM monitoring	n/a
1 week			
4	Phone	QUIT DATE; counseling session 3 of 5; begin 4 weeks active mCM monitoring; begin nicotine replacement therapy (NRT)	n/a

1 week			
5	Phone	Counseling session 4 of 5; continue active mCM monitoring	n/a
1 week			
6	Phone	Counseling session 5 of 5; continue active mCM monitoring	n/a
2 weeks			
7	Phone or Text Message	Begin 1 week mCM wash-out period	Up to \$798 mCM compensation

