2 weeks post-mCM treatment follow-up			
8	Phone	Questionnaires; equipment return; treatment adherence measures	\$50 for equipment return
3 months after Session 1			
9	Phone/Lab	Questionnaires; return to lab and provide a saliva sample if abstinence reported	\$25 for assessment; \$50 for saliva sample
6 months after Session 1			
10	Phone/Lab	Questionnaires; return to lab and provide a saliva sample if abstinence reported	\$25 for assessment; \$50 for saliva sample
TOTAL COMPENSATION POSSIBLE			\$1098

Once a participant reports to the laboratory to begin the study, the study staff member obtaining consent will explain the study in detail, provide the participant with an IRB-approved written consent form explaining the procedures and risks, and answer any questions. The initial consent process and documentation takes place in a quiet, private office at DUMC (Hock Plaza space), and participants are given the chance to thoroughly read the consent prior to participation. Participants are given a copy of the signed informed consent form, and are given phone numbers to call if they have additional questions about the consent form or the research, if they have any problems during the study, or if they have questions about participating in research studies in general. No study procedures will begin until informed consent has been obtained.

After providing informed consent, potential participants will provide a breath sample to assess CO level, and will complete measures (see Measures section herein) regarding mood, exercise and smoking history, and sociodemographic data. Urine samples will also be used to screen for illicit drug use (to document use). Because the study drugs are each Category C drugs, urine pregnancy tests will also be completed for women of childbearing potential. We have developed a short interview for female participants; this interview will help us determine which female participants must have a urine pregnancy test, and when the test should be done. Female participants of childbearing potential who are not pregnant must agree to use appropriate

contraception during the course of the study, and to notify study staff if they become pregnant during the study.

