All enrolled participants will receive a tele-health intervention that combines evidence-based telephone cognitive behavioral therapy (CBT) for smoking cessation, access to nicotine replacement therapy (NRT) and bupropion, and intensive CM therapy administered via a smart-phone based application (mCM). The treatment components are separately described below. After randomization, participants will be given study equipment, including a smartphone (with the condition-appropriate app already installed), CO monitor, Jawbone UP2 fitness tracker, and a high-accuracy digital bathroom scale. Participants will receive training in use of all equipment at the screening visit. Participants will also complete session 1 of the CBT in person in order to enhance therapeutic rapport-building.

Study Devices. Smart phones to be used in this study are the DROID MAXX 2. The phone has an octa-core 1.7 Ghz processor, 2 GB RAM, and 5.5" full HD display. The operating system (OS) being utilized for the smart phones is Android 5.1.1 Lollipop, see FIPS 140-2 certificate 1998. The STEP UP mobile phone app is an adaptation of smoking-cessation mCM mobile phone apps that have been used in several IRB-approved studies (PRO0031703, PRO0050835, PRO0048990, PRO0061683, PRO0062101) with expert input from [name]. [name] is a Professor in the Duke University Department of Medicine and the Associate Director of Research at the Durham VA Geriatric Research, Education, and Clinical Centers. [name] is an exercise physiologist and her specialization is in the design and execution of behavioral clinical trials of physical activity.

We have modified the app to include physical-activity monitoring components and feedback. Step-tracking will be implemented via a Fitbit Flex 2 fitness tracker. The Fitbit Flex 2 is a light-weight wristband capable of tracking physical activity, including steps. Data are transmitted from the Fitbit Flex 2 to the smart phone via Bluetooth technology and the Fitbit Flex 2 App. Our STEP UP mobile app will pull the data from Fitbit's servers and integrate the data with smoking cessation data so that participants and study staff can monitor progress towards step goals. Within the STEP UP app, progress toward daily step goals will be conveyed twice daily at semi-random intervals and will also be available on-demand. The mCM manual includes the participant instructions, payment schedules, and app screenshots.

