Missing Data. Because the main predictors of interest, treatment group and demographics, are collected at baseline, we do not anticipate much missing data. We do, however, anticipate

missing values in the longitudinal outcomes owing to dropout, an inability to reach participants, or item non-response. Multilevel modeling (MLM), which employs maximum and pseudo-maximum likelihood estimation, is proposed to address this issue. MLM uses all available data; as such, it can accommodate data missing at random. Because individuals with the least missing data have the most influence on model results, analyses will be conducted to determine whether missingness is systematic (i.e., associated with individual differences in either baseline parameters or time-related changes in observed variables). If data are deemed not to be missing at random, additional approaches to deal with missingness in the response will also be explored, including imputing missing values by multiple-imputation procedures as described by Schafer (Schafer & Graham, 2002).

The feasibility and acceptability of STEP UP will be assessed. Content analysis of the cohort interviews will yield descriptive data regarding participants' perceptions of specific components of the treatment at each development phase. Participant feedback will be used to evaluate the user experience so that the phone app and counseling procedures can be enjoyable to the target population. We will describe participant recruitment (proportion of participants screened/enrolled), participant treatment retention (number of sessions completed, drop outs). Acceptability of STEP UP will be assessed via descriptive analyses of the ordinal-level outcomes on the treatment-acceptability survey completed at the conclusion of the RCT. Participants' responses to open-ended questions will be compiled for content analysis. In addition to evaluating participant satisfaction, we will describe use of mHealth applications (adherence with mCM videos, compliance with wearing the step-tracker, comfort with the app), medication adherence, participant smoking-cessation and physical-activity content knowledge before and after treatment, and treatment fidelity. All of these data will provide critical information prior to planning a larger RCT.

References

Abrahms, J.L. & Allen, G.J. (1974). Comparative effectiveness of situational programming, financial pay-offs and group pressure in weight reduction. *Behavior Therapy*, 5, 391-400.

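### The protocol describes one arm in some sections and randomised arms in others, and the conflict reaches the analysis: state the design once, align the text, and fix how the abstinence proportion is counted

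*Combined protocol and SAP*

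**What the plan says.** Text that fits one group:

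- End of Background: "The purpose of this pilot project is to evaluate the feasibility, acceptability, and efficacy of STEP UP". No comparator is named.
- Methods, Participants: "We plan to enroll 15 participants in order to reach a goal of 10 study completers". No split is given.
- Study Procedures, Table 1: one schedule. At the quit date the entry includes "begin 4 weeks active mCM monitoring", and the table closes with one line, "TOTAL COMPENSATION POSSIBLE", of $1098.
- Study Procedures, text: "All enrolled participants will receive a tele-health intervention that combines evidence-based telephone cognitive behavioral therapy (CBT) for smoking cessation". The same sentence includes mobile contingency management (mCM) in the package.
- Mobile CM Procedures and Participant Reimbursement: one mCM ceiling ($798) and one overall total ($1098).
- Data Analyses: interviews with a cohort, mostly descriptive summaries, and no between-group test.

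Text that presupposes more than one group:

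- Study Procedures: "After randomization, participants will be given study equipment", including a phone "with the condition-appropriate app already installed".
- Cognitive Behavioral Therapy for Smoking Cessation: a comparison condition is named beside STEP UP, and both get the manual and five counselling sessions.
- Text-Messaging Support: messages go to two arms.
- Data Analyses, Missing Data: "Because the main predictors of interest, treatment group and demographics, are collected at baseline".
- Data Analyses, acceptability paragraph: the survey is timed to the end of a randomised trial, whereas Measures of Treatment Acceptability times it to the end of treatment.
- Data and Safety Monitoring Plan: study groups in the plural. This is weak support by itself.

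The primary endpoint is self-reported and bioverified prolonged abstinence at 3 and 6 months. Proportions are planned for categorical variables. For missing longitudinal outcomes the plan proposes multilevel modelling under a missing-at-random assumption. If that assumption is judged to fail, other methods, including multiple imputation, are to be explored.

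**The concern.** These passages are all current text, and they cannot all be true. The conflict matters because it reaches the analysis section, where treatment group is named as a main predictor. An analyst following the plan would have either a predictor that does not vary or a comparison whose control condition is only partly described. A later reader could take a one-group abstinence rate for one arm of a randomised trial.

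The second issue exists under either design. The primary endpoint is a proportion in a very small sample, and the plan does not say over whom it is taken or how a person without an outcome counts. With 15 people, that choice visibly moves the headline figure.

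**Working it through.** **1. Do the plan's own figures show one group or two?** Payments (Participant Reimbursement): 100 + 798 + 50 + 2×25 + 2×50 = 1098. This equals the single stated total and includes the full mCM earnings. No second ceiling appears for people in another condition. Enrolment: 15 for 10 completers implies 1 − 10/15 = 33.3% attrition, so the two figures agree with each other. There is no per-arm number, allocation ratio, power or effect size.

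**2. What follows under each reading?**

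| Reading | Treatment group as a predictor | What is missing |
|---|---|---|
| One arm | Same value for all 15; no effect can be estimated. Demographics remain usable. | Nothing by way of contrast; the predictor and the randomization wording do not belong |
| Two arms | Varies, so could be estimated | Comparator's mCM and app content, allocation method, arm sizes, the contrast itself |

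The sentence on all enrolled participants could by itself fit two arms that both get mCM through different apps. Taken with the undivided 15, the single schedule and the single ceilings, it favours one arm.

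**3. If two arms were meant, could 15 people support a comparison?** The plan gives no effect size, so this is illustration only: exact Fisher test, two-sided 5% (assumed), 7 versus 8 people.

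| Assumed abstinence rates | Power, 7 vs 8 | Power, 5 vs 5 |
|---|---|---|
| 25% vs 52% | 12.4% | 6.6% |
| 10% vs 60% | 41.5% | 22.4% |
| 20% vs 80% | 64.8% | 37.6% |

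The 25% and 52% are the rates quoted by adherence level in Measures of Treatment Feasibility and Adherence, borrowed only as a plausible pair. At those rates 80% power needs about 50 per arm (normal approximation).

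**4. How far can the denominator and missing rule move the primary proportion?** Let x be the number verified abstinent and m the number of the 15 with no outcome. Missing counted as smoking gives x/15; observed cases give x/(15 − m); the best case gives (x + m)/15. Both x and m are assumptions. The value m = 5 comes from 15 − 10 and applies only if all five people beyond the completer goal lack an outcome; the plan does not define a completer.

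| x | m | Missing = smoking | Observed cases | Best case |
|---|---|---|---|---|
| 4 | 0 | 4/15 = 27% | 4/15 = 27% | 4/15 = 27% |
| 4 | 2 | 4/15 = 27% | 4/13 = 31% | 6/15 = 40% |
| 4 | 5 | 4/15 = 27% | 4/10 = 40% | 9/15 = 60% |
| 2 | 5 | 2/15 = 13% | 2/10 = 20% | 7/15 = 47% |
| 6 | 5 | 6/15 = 40% | 6/10 = 60% | 11/15 = 73% |

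With m = 5 the observed-case rate is always 15/10 = 1.5 times the all-enrolled rate.

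**5. Is the number enrolled itself fixed?** Not quite. Study Procedures still calls people potential participants after consent, while they are being tested. Pregnancy is an exclusion, and the feasibility text separates screened from enrolled. Whether someone who fails screening after consent is in the denominator is not stated.

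**The case against.** The best defence is that this is a small pilot with leftover wording from a two-arm template. Much of that stands. Data Analyses is mostly descriptive, contains no between-group test, refers to interviews with a cohort, and says the data will inform the planning of a bigger randomised trial. The equipment sentence that mentions randomization also lists a Jawbone tracker, while the rest of the protocol uses a Fitbit, which suggests that the sentence was not fully updated. A reader might infer that the design is unknowable, or that a control arm was planned and left out. The documents support neither: they lean towards one arm. They also promise no comparative conclusion; the purpose statement speaks only of efficacy in a pilot. But the remark about a bigger trial fits a small randomised study as well as a single-arm one, and the two-arm wording recurs in the procedures, treatment and analysis sections. It is not one stray word.

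On missing data, a reader might infer that the plan is silent. It is not. Abstinence at 3 and 6 months fits its description of longitudinal outcomes, to which multilevel modelling applies. The gap is narrower: no denominator for the reported proportion, no rule for a missing saliva sample, and no fixed choice once data are judged not missing at random. Nor do the documents require that missing be counted as smoking, or that modelling be barred from the primary endpoint. That is the sponsor's choice.

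**Conclusion.** The contradiction is real and must be resolved before analysis. As written, the treatment-group effect is inestimable with one arm and has no defined contrast with two, so the efficacy purpose cannot support a comparative conclusion under either reading. That the single-arm reading is likelier is an inference from the undivided sample, schedule and payments; only the sponsor can confirm it.

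The denominator point is secondary and does not depend on the design. Its size, assuming 4 abstinent and 5 of 15 missing, is a range from 27% to 60%, with 40% on observed cases; it shrinks to nothing if no outcome is missing. The width of a confidence interval at n = 15 is not a measure of this defect, since no change of wording alters it.

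**What to change.** **Design.** The sponsor confirms the design and states it once in Methods.

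*If single-arm:*
- Background, purpose: restate efficacy as preliminary, uncontrolled estimates of abstinence.
- Study Procedures: remove the reference to randomization, and name the STEP UP app in place of "with the condition-appropriate app already installed".
- Cognitive Behavioral Therapy and Text-Messaging Support: replace the references to a comparison condition and to two arms with all participants.
- Data and Safety Monitoring Plan: change study groups to study.
- Data Analyses: delete treatment group as a predictor, and time the acceptability survey to the end of treatment, as Measures of Treatment Acceptability already does.

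*If two-arm:*
- Reconcile the one-group text in the purpose statement, Participants, Table 1, Study Procedures, Mobile CM Procedures and Participant Reimbursement.
- Describe the comparison condition's mCM and app content in the counselling section, and state the allocation method and number per arm.
- Report the difference in abstinence with a 95% confidence interval, labelled as unpowered.

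**Abstinence proportion (either design).** In Data Analyses, with both endpoint sections aligned:
- Report the count over all enrolled, with an exact 95% confidence interval, at 3 and at 6 months (by arm if there are two).
- Define enrolled, including whether post-consent screen failures count.
- State one rule for missed contacts and for reported abstinence without a saliva result, and say how it relates to the multilevel-modelling and imputation text. Missing counted as smoking is one option.
- Give observed-case and best/worst-case bounds as sensitivity analyses.

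**Cost.** Single-arm: wording only, with no new data or visits. Two-arm: wording plus comparator and allocation details that only the sponsor can supply. The downside is that no comparative efficacy claim can be made and, depending on the rule chosen, the reported abstinence rate may be lower.

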Smoking-Cessation Outcome Measures and Biochemical Verification. Our choice of primary and secondary smoking endpoints follows recommendations by the Society of Research on Nicotine and Tobacco (SRNT; Hughes et al., 2003). Self-reported and bio-verified prolonged abstinence at the 3- and 6-month follow-ups will be the primary endpoints. Prolonged abstinence will exclude tobacco use in the first 2 weeks following the quit date (Hughes et al., 2003). Self-reported prolonged abstinence will be verified by cotinine assay. CO and saliva samples will be collected from participants who report prolonged abstinence at each follow-up. Saliva samples will be sent to the Duke University Nicotine Research Program to be analyzed for the presence of cotinine using a standard cut point of 10 ng/ml to determine abstinence. A blind sample of 5% will be rerun to assure test accuracy of saliva samples. Secondary smoking outcomes will include 7- and 30-day point prevalence abstinence at each assessment, where abstinence is defined as no tobacco use in the prior 7 or 30 days respectively. Additionally, participants will be asked if they have made one or more quit attempts in each follow-up period using a time-line follow back method (Lewis-Esquerre et al., 2005). We have recent experience using this method to assess daily smoking behavior (Carpenter et al., 2015).

Potential Risks

There is a risk of discomfort or distress in answering questions on the study measures. However, distress and discomfort related to questionnaire completion is usually temporary and well-tolerated. Risks also include discomfort related to quitting smoking. Quitting smoking may cause difficulty concentrating, poor sleep, increased appetite, anxious or depressed mood, and craving for cigarettes. Participants will be offered NRT, and there are risks associated with the use of NRT. Minimal risks associated with wearing a nicotine patch include skin irritation, dizziness, lightheadedness, increased heart rate or blood pressure, nausea or vomiting. If a participant indicates a contraindication to NRT (e.g. uncontrolled hypertension), medical clearance for NRT will be sought from the participant's primary care physician and/or the study physician. If a participant with a seizure disorder, history of or current hepatitis and/or cirrhosis, renal

impairment, and/or uncontrolled diabetes wishes to enroll in the study, he/she will not receive contraindicated medications.

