Self-reported and bioverified prolonged abstinence from smoking at the 3 and 6-month follow-up will be the primary end-point. Prolonged abstinence will exclude tobacco use in the first two weeks following the quit date to give participants time to achieve initial abstinence (Hughes et al., 2003). Self-reported prolonged abstinence will be verified by cotinine assay, a metabolite of nicotine in the saliva. Saliva samples will be collected from participants who report prolonged abstinence at each follow-up. They will be mailed to Salimetrics LLC for saliva cotinine assays. Saliva samples will be analyzed for the presence of cotinine using a standard cut point of 10 ng/ml to determine abstinence. A blind sample of 5% will be run again to assure test accuracy of saliva samples. Secondary smoking outcomes will include 7- and 30-day point prevalence abstinence at each assessment, where abstinence is defined as no tobacco use in the prior 7 or 30 days, respectively.

Data Analyses

Descriptive statistics will be used to summarize all study variables, including smoking history and current use, nicotine-dependence level, self-efficacy, readiness to change, and social support. For continuous variables, means, standard deviations, ranges, and histograms will be generated. For categorical variables, frequencies and proportions will be generated. Individual and mean trajectory plots of the longitudinal outcome variables will be constructed to understand their general trends over time (i.e., post-treatment, 3- and 6-month follow-ups). We will examine all variables to determine if parametric distributional assumptions (e.g., normality for the continuous variables) are valid. Variables not meeting distributional assumptions will either be transformed or modeled using non-parametric or semi-parametric methods (e.g., quasi-likelihood methods; McCullagh & Nelder, 1989). In order to describe the compliance/completion of the sample in terms of smoking-cessation aids and intervention completion, these variables will be summarized. In terms of descriptors for outcome measures, we will record number of quit attempts, quality of life, and number of weekly steps, and utilize time-line follow-back data to identify when participants may have lapsed. Potential covariates (e.g., age, gender, minority status) will be evaluated for inclusion in models. If any of these variables have a significant bivariate effect on treatment outcomes, they will be entered first in statistical models.

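### The plan's check for data not missing at random cannot detect that condition, its one named fallback assumes missing at random again, and the primary abstinence proportion has no stated denominator

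*Combined protocol and SAP*

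**What the plan says.** All references are to the combined protocol and SAP.

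**Missing data.** The Missing Data paragraph under Data Analyses expects "missing values in the longitudinal outcomes owing to dropout, an inability to reach participants, or item non-response". Its main method is multilevel modelling, on the ground that "MLM uses all available data; as such, it can accommodate data missing at random". It then plans to examine whether missingness is systematic, which it defines as "associated with individual differences in either baseline parameters or time-related changes in observed variables". The next sentence gives the trigger and the response: "If data are deemed not to be missing at random, additional approaches to deal with missingness in the response will also be explored". The list of approaches is open, but the only one named is "imputing missing values by multiple-imputation procedures", with a literature reference. No other criterion for the judgement is given.

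**Primary endpoint.** It is stated twice. Smoking-Cessation Outcome Measures and Biochemical Verification says: "Self-reported and bio-verified prolonged abstinence at the 3- and 6-month follow-ups will be the primary endpoints". Outcome Measurement and Biochemical Verification says: "Self-reported and bioverified prolonged abstinence from smoking at the 3 and 6-month follow-up will be the primary end-point". For summarising a yes/no variable, Data Analyses says: "For categorical variables, frequencies and proportions will be generated". The plan does not say whether the denominator is everyone enrolled, everyone reached or the completers. It does not say how a participant who is never reached is counted, or whether abstinence is one of the longitudinal outcomes that go into the multilevel model.

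**The concern.** There are two linked problems.

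First, the rule for moving beyond MAR does not work. The feared mechanism in a cessation study is that people are lost because they are smoking, in a way the recorded data do not show. A comparison on recorded data cannot identify that. If the trigger fires anyway, the remedy named rests on the assumption that has just been rejected.

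Second, the primary result can be calculated in more than one way. The endpoint wording suggests that someone with no report and no confirmed sample cannot be a success, which leads to an all-enrolled denominator. The Missing Data paragraph treats people who cannot be contacted as missing, which leads to leaving them out or modelling them. Two analysts following the plan could report different primary rates from the same data.

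This matters because efficacy is one of the three purposes of the pilot given at the end of the Background.

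**Working it through.** **Step 1. What the plan supplies.** The Participants section plans 15 enrolled to obtain 10 completers. Back-solved, that is 1 - 10/15 = 33.3% attrition, and 10/(1 - 1/3) = 15. The plan states no dropout rate, does not tie the 10 to the 3- or 6-month visit, and gives no expected abstinence rate. There is no figure to reproduce, so the rates below are assumed and only illustrate.

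**Step 2. What the check can distinguish.**

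| Mechanism | Loss depends on | What the check may find | Multilevel model and standard imputation |
|---|---|---|---|
| Missing completely at random | nothing relevant | no association | valid if the model is right |
| MAR | observed variables | association | valid if the model is right |
| Not missing at random | unseen smoking status as well | association or none | generally biased |

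An association does not separate the second row from the third. Its absence does not separate the first from the third. Under the plan's rule, an ordinary MAR pattern would be declared not MAR, and a harmful pattern could pass.

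**Step 3. A pattern that passes.** Let true abstinence be p = 0.30, and let smokers and abstainers be lost with probabilities rs and ra. Suppose the observed variables carry no information about smoking status or loss. The check then has nothing to find, and the MAR estimate equals the available-case rate:

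p(1 - ra) / [p(1 - ra) + (1 - p)(1 - rs)]

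- rs = 0.50, ra = 0: 0.300/0.650 = 46.2%
- rs = 0.45, ra = 0.05: 0.285/0.670 = 42.5%
- rs = 0.40, ra = 0.17: 0.249/0.669 = 37.2%

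**Step 4. The denominator.** Let x be the verified abstainers and m the number missing out of 15. The available-case rate is x/(15 - m). The all-enrolled rate with missing counted as not abstinent is x/15. Their ratio is 15/(15 - m), whatever x is. The upper bound is (x + m)/15, so the bounds are m/15 apart.

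| m | Ratio | Width of bounds (points) |
|---|---|---|
| 1 | 1.07 | 6.7 |
| 2 | 1.15 | 13.3 |
| 3 | 1.25 | 20.0 |
| 4 | 1.36 | 26.7 |
| 5 | 1.50 | 33.3 |

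Example with x = 4, m = 5: available-case 4/10 = 40.0% (exact 95% interval 12.2 to 73.8%); all-enrolled 4/15 = 26.7% (7.8 to 55.1%); upper bound 9/15 = 60.0%.

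**Step 5. Direction.** In the same example, let a proportion d of the five missing be abstinent. The truth is (4 + 5d)/15. The available-case error is 0.40 - (4 + 5d)/15. The error from counting missing as smoking is 4/15 - (4 + 5d)/15 = -d/3.

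| d | Available-case error (points) | Missing = smoking error (points) |
|---|---|---|
| 0 | +13.3 | 0 |
| 0.1 | +10.0 | -3.3 |
| 0.2 | +6.7 | -6.7 |
| 0.4 | 0 | -13.3 |
| 0.6 | -6.7 | -20.0 |

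Neither convention is safe alone.

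**The case against.** The strongest reply is that the endpoint already settles the matter: it needs both a report and biochemical confirmation, so someone never reached cannot be a success. That is a fair reading of the numerator, and it probably also disposes of the unverified self-report. But it conflicts with the Missing Data paragraph, which classes the same people as missing, and it still leaves the denominator unstated.

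Second, if abstinence is summarised only as a simple proportion, the faulty check and fallback never touch it. That stands. They then affect only modelled outcomes, and the denominator is the gap for the primary endpoint.

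Third, the fallback list is open and cites a source that may describe other methods. This also stands, so the claim is limited to the one method named.

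Fourth, this is a 15-person pilot. The exact intervals are much wider than the 13.3-point gap in the example. Loss to follow-up is to be reported as a feasibility measure, so a reader could rebuild an all-enrolled rate if losses were given by visit. This limits the consequence but does not repair the rule.

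A reader might infer more than the documents support:

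- That the plan will overstate abstinence. Step 5 shows that the direction depends on the unknown status of those lost.
- That a one-third loss at follow-up is planned. The 15-to-10 figure is a recruitment target.
- That the abstinence rate is said to feed the larger trial. The sentence on planning that trial closes a paragraph on feasibility, acceptability, adherence and fidelity, which does not list abstinence.

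**Conclusion.** The missing-data rule is wrong as written and should be fixed. It takes associations with observed variables as evidence against MAR, although MAR allows them, and the only remedy it names makes the MAR assumption again in its standard form. This conclusion is logical and needs no assumed numbers.

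For the primary endpoint, the defect is an unstated denominator and two conflicting readings of a participant who is never reached. The size is a ratio of 15/(15 - m) between the two natural rates: 1.07 with one missing and 1.5 with five. The ratio is exact for 15 enrolled, but m is assumed, and so are the percentages in the working.

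Importance rests on efficacy being a stated purpose. It is tempered by the sample size, the wide intervals and the absence of any stated test of abstinence. The documents do not support saying that the primary result will be biased in a given direction, or that the multilevel model will be applied to it.

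**What to change.** - **Primary endpoint.** Report prolonged abstinence at 3 and 6 months over all enrolled participants, counting those not reached or not verified as not abstinent. Beside it, always show the numbers missing and unverified, the available-case rate, and best/worst-case bounds (or delta-adjusted imputation) for those not reached.
- **7- and 30-day point prevalence.** Use all enrolled, missing counted as smoking, and the same bounds. Do not count an unverified self-report as smoking, because verification is not planned for these outcomes. Session 8 is a telephone visit with no CO or saliva sample listed in Table 1, although Table 2 schedules a 7-day measure at post-treatment. The two endpoint sections collect samples only from those who report prolonged abstinence. A blanket rule would turn every post-treatment self-reported abstainer into a smoker.
- **Missing Data paragraph.** Keep the observed-variable comparison only as a description of who was lost. Label the multilevel model and standard multiple imputation as MAR analyses, and state whether they apply to abstinence. Replace the trigger with the bounds or delta-adjusted analysis, reported in every case.
- **Narrowing the bounds.** Use recorded smoking after the two-week grace period to settle a missing participant's status only if a relapse criterion is stated first. The plan gives none.

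The cost is SAP wording and one small table; no new data are needed. The drawback is a headline rate that is lower and may be biased low, by 3.3, 6.7 or 13.3 points if five are missing and 10%, 20% or 40% of them are in fact abstinent. Counting missing as smoking is a convention that these data cannot test; the bounds make its effect visible.
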